7.2.3 Data privacy protection

Personally identifiable information will be maintained confidentially under strict SOPs, complying with all applicable international regulations. Study team members with access to PII will sign a confidentiality agreement prior to collecting or accessing any of the data. Each participant will be given a different unique alphanumeric identifier for each study in which he/she is associated. Voice recording files and written notes that refer to the same participant interview will be labelled using the same identifier. The IT infrastructure will provide password protected devices, laptops with encrypted hard drives, fileserver with customizable access rights, and documented and audited access right management. All transfer of data via the internet will be done via secure, encrypted connections.

All quantitative data collection instruments will be stored in closed, locked file cabinets with restricted access. The EDC platform will be encrypted and password protected. All study databases will be safeguarded against unauthorized access by established security procedures. A double coding procedure will ensure that participant re-identification is not feasible. The name of the facility of enrolment, geographic information and some elements of dates related to facility visits will also be de-identified. To further prevent re-identification of individuals (patients, caregivers and healthcare providers), where appropriate, data will be de-identified so that their level of granularity that does not allow indirect identification of an individual. In addition, the data imported from another study datasets will be processed (e.g., aggregated data, categorization of numeric values) so that a unique combination of facility and individual characteristics does not allow indirect identification of an individual.

Voice recordings, photos and videos, as well as GPS mapping, will be deleted from the devices after transcription, translation and digitalization. Transcriptions and translations of audio data and typed-up field notes will be stored on the central database in password protected folders accessible only to authorized qualitative researchers. Hand-written notes and drawings will be stored in locked filing cabinets in an area with restricted access. During the coding process qualitative data uploaded into the coding software will be manually de-identified (i.e. replacing names, locations, other personal identifiers) ensuring that only de-identified interview material is stored in the programme.

7.2.4 Data quality assurance and control

Quality assurance activities across all studies will be more intense during study start-up to ensure quality data practices are instituted from the start of the trial. Further details will be given in the DMP and SOPs.

All research assistants will be trained to provide information and seek written consent using the information and consent form. Separate trainings will cover all aspects of quantitative data collection and all aspects of qualitative data collection. A competency assessment using scenarios will be done before commencing field work.

Data reconciliation between the different visits of the same child will be one of the most crucial data quality activities in the pre-post study. Specific procedures will be developed for this purpose. To identify repeat visits of children that may re-attend the study facility where they enrolled, or any other study facility during the follow-up period, participants will be given a study card (or sticker) with a unique ID number. Retrospective search for data at referral level will be restricted to facilities within the geographical area where the study is running and will be targeted to include only children reported to have attended hospital by the caregiver at follow-up and those lost to follow-up. The name of the referral facility will be requested during the follow-up call. If available, it should further restrict the scope of the search and the probability of negative matches when cross-checking the participant identity. Children who re-attend any study facility more than 28 days after their previous enrolment will be enrolled for the new disease episode and given a new ID number. If available, the old ID number will be recorded to facilitate linking of the different disease episodes. Data to be potentially reconciled will be flagged by automated cross-check of a set of personal identifiers. Given that personal identifiers may not be identically recorded at each visit, fuzzy matching methods will be used to calculate a score of similarity between records and likelihood that they relate to the same child. Reconciliation of records with high similarity scores will be manually validated.

The validity of quantitative data will be ensured through data definitions and field restrictions in the electronic systems. Acceptable error rates in critical quantitative data will be established during the pilot phase and documented in the DMP. Pre-defined automated high-frequency checks will be performed including checks of completeness and indicators of other irregularities such as completion time. Reports will be shared with individual quantitative research assistants and their supervisors. In addition to reviewing automatically generated reports for their supervisees, supervisors will perform random accuracy checks of research data compared to available source data. In the pre-post study, quantitative research assistants responsible for the Day 7 call will be audited through random checks of phone logs and repeat phone calls. After confirmation that the study databases contain all expected data, an internal review will check their accuracy and quality. Once all the required data quality assurance and control have been completed and passed, the study databases will be “locked”.

During the pilot phase, qualitative tools will be translated and back translated, and tested using cognitive interviewing to ensure questions asked are understood as intended and felt to be

appropriate. Regular quality checks of transcriptions and translations will be conducted by the qualitative researcher in each country.

7.3 Statistical methods

Statistical methods will be described in detail in the Statistical Analysis Plan (SAP). We will conduct all analyses described below per country, in addition to a pooled cross-country analysis. Quantitative analyses will be conducted using Stata (or alternative statistical analysis software, depending on investigator for certain country-specific or sub-study specific analyses).

7.3.1 Quasi-experimental pre-post study

Analysis will include all eligible, consenting and enrolled children. Baseline characteristics will be described by country and across all study time points with summary statistics such as median and interquartile range or number and percentage. Outcomes will be described for each time period using summary statistics and results from the pre-intervention period and the post-intervention period will be compared. The two primary outcomes will be assessed using a random effects logistic regression models with the cluster (facility) included as a random effect. All models will be adjusted for individual-level baseline characteristics such as gender and age whose distribution at the facility may have changed between the time periods. Results will be reported with odds ratios and 95% confidence intervals (CI). Binary secondary outcomes will be evaluated in the same way. Continuous secondary outcomes will be assessed using random effects linear regression models, reporting adjusted mean differences between time periods with 95% CIs.

We will conduct planned subgroup analysis of the primary outcomes to assess for potential effect modification in variables such as clinical presentation (particularly cough / difficulty breathing) and diagnosis (particularly severity classification). If these variables are found to be balanced between the two time periods, effect modification will be assessed by incorporating an interaction between the time period and the variable in the model, acknowledging that power will be low. Additional individual or facility level characteristics to be considered in the model will be further detailed in the statistical analysis plan (SAP).

We will conduct the primary analysis on all visits (for visits by the same child, this implies visits greater than 28 days apart as per the exclusion criteria). However, we will conduct a sensitivity analysis excluding repeat visits of an individual child within the same quarter, to address the possibility that outcomes of children attending for more than one disease episode are correlated and impact the interpretation of the study. Due to the challenge in correctly identifying all repeated visits, the fairly low likelihood of repeat visits (based on available literature) and the acuity of the majority of sick child visits, we do not expect these analyses to produce very different results. We will conduct sensitivity analyses for measured and unmeasured confounders over time to assess robustness of the findings, which will be detailed in the SAP.

An exploratory interrupted time series analysis will be conducted to assess change over time.

7.3.2 Routine data

Relevant aggregated data from routine HMIS will be used to monitor trends over time in all facilities and administrative regions where the project is running (i.e. both study facilities and non-study facilities) pre- and post-intervention.

Routine CDSA clinical data will be used to conduct descriptive analysis on the use of pulse oximetry and prevalence of hypoxaemia in non-pre-post study facilities post-intervention. Univariate and multivariate analyses will assess factors associated with hypoxaemia such as age, sex and clinical presentation. This data will also be used to estimate health outcomes in facilities not involved in the pre-post study, building a model from the data collected in facilities that are involved in the study. This estimate will then be gauged against HMIS data to identify indicators for longer term monitoring of the intervention.

7.3.3 Other mixed methods studies

Quantitative

Descriptive analysis will be conducted of the data obtained from the SPA studies by country, facility type and location and child and healthcare provider characteristics. Indices of adherence to key practices will be described and compared between and time points (pre-intervention and the 4 post intervention time points). Time-flow data will also be compared between pre-intervention and each of the post-intervention periods. Effect modifiers will be explored.

Monitoring and evaluation data from non-pre-post study intervention facilities will be analysed along with aggregated HMIS data, with comparison to pre-post study facilities to draw inferences on the impact and uptake of the wider programme of implementation.

Qualitative analyses

Quality assurance steps for transcription and translation will be built into the process.

Qualitative data will be transcribed verbatim using modified transcription rules by Kallmeyer and Schütze⁵¹ and translated into English and/or French. A random sample of transcripts and translations will be quality checked by listening to audio-recordings and back translations and measures taken accordingly. After familiarization with all interviews/FGDs, an experienced qualitative researcher will code the transcripts using a qualitative coding software. A random sample of a total of 10-15% of the qualitative interviews will be coded using the framework analysis by Gale et al.⁵² following an inductive and deductive approach; in-vivo codes will be created where applicable. The final draft code tree will be exported, codings deleted and the same interviews coded by a second and independent qualitative researcher for inter-rater reliability check. The Kappa-Cohen value will be calculated. Differences in coding will be discussed and a joint solution developed. A Kappa-Cohen value above 80% will allow using the code tree after minor adaptations based on joint agreements by the two coders and for final coding. The finalized code tree will be used to code the entire material. Finally, each code and each sub-code with its coded material will be exported into excel tables. A team of qualitative

researchers will review the tables and jointly analyse the data identifying patterns, similarities, and differences as well as change over time. Secondary analysis of data (i.e. including comparison of final code trees) from all study countries may be conducted jointly and findings compared across countries.

Document review

The document review data will be entered into a grid with predefined categories in line with process evaluation criteria. Data will be triangulated against qualitative and quantitative data collected.

Process evaluation

The process evaluation will draw on data from the various sub-studies to describe the context, implementation process and mechanisms of impact as outlined in **Fig 8**.

[figure not shown]

Fig 8. Overview of MRC process evaluation of complex interventions (Image credit Moore et al)³⁵

7.3.4 Cost and modelled cost-effectiveness study

When all the cost components have been collected, the data will be aggregated or collated in Excel. Once the summary is completed, a cost profile of the programme activities will be derived and after the total costs of the programme have been calculated, the unit costs will then be derived (i.e. total costs divided by the sample size). These profiles are useful in highlighting major cost components (and thus identifying potential areas where improvements in efficiency may have significant impact on costs). For this evaluation, analysis will focus on full costing and incremental costing approach. Total, average and incremental costs per year will be estimated. Costs associated with increasing the oxygen saturation referral threshold will be estimated based on the additional proportion of children meeting referral criteria.

When available, effectiveness data will be combined with the cost data and cost per DALY averted will be estimated. Effectiveness will be modelled using the information on severe outcomes such as mortality, and secondary hospitalization, adjusting as far as possible the level of severity of illness of the child at presentation.

At primary care facilities, these will include measurements (when taken by healthcare providers) such as anthropometry, respiratory rate, temperature and routine investigations where available (e.g. haemoglobin, CRP), and oxygen saturation (post-intervention/in intervention arms). We will also use diagnosis and severity classification recorded by primary care providers.

At hospital level, we will also utilize the same measurement data, and other vital sign data (such as a paediatric early warning score if recorded), decision to admit, intensive care and / or ventilation, provisional and final diagnosis, admission outcome (discharge, death, left against medical advice) and length of hospital stay. We will then use these indicators, along with mortality from phone call follow-up data by Day 28, to predict probability of mortality based on available literature. The DALY calculation will be based primarily on probability of mortality over a relatively short horizon (to be determined based on a review of literature, likely between three and six months to reflect the time windows used in post hospital discharge mortality studies). The types of illnesses considered do not typically lead to long-term disability, and the duration of illness is too short to have a big impact on DALY calculations. We will not use age weights: we will use GBD (2017) DALYs,⁵³ and we will not use country-specific disutility data, both since we are unsure these exist for all the countries, and they render cross-country comparisons more difficult.

Sensitivity analysis

As not all data will be available precisely, we will explore possible assumptions using sensitivity analysis which will assess how the estimates would react to percentages changes in the value of the assumptions. It can help the reviewer to determine which parameters are the key drivers of a model's results. Guidelines and standard textbook recommend that economic evaluations should include sensitivity analysis.⁵⁴ We will undertake one-way sensitivity analysis of key parameters using the major outcome and cost parameters. Typically. Such analyses are more sensitive to the assumptions about outcomes, and for this we have to rely on the best judgement of the epidemiologists.

8 Monitoring

All studies will be conducted in accordance with the protocol and international and applicable national regulatory requirements. The Clinical Operations Unit within the Department of Medicine at Swiss TPH will provide training of trainers on ethics and monitoring for research partners if required. Country research partners will be responsible for setting up and carrying out the monitoring plan, in consultation with Swiss TPH. This will include regular monitoring of screening data, consent, recruitment rates and missing data on primary and important secondary endpoints. Outliers on key indicators will trigger site visits.

9 Ethics and dissemination

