6.6.1 Quasi-experimental pre-post study

The sample size for the quasi-experimental pre-post study is calculated separately for each country, based on comparison between pre- and post-intervention periods.. The following assumptions are used:

- ξ power 80%
- ξ alpha 0.05
- ξ pre-intervention referral to a higher level of care 3% (based on informal estimates from country research teams and SPA data from various countries), with a minimum detectable difference of 50%
 - We have chosen a large detectable difference for referral from primary care as not all children referred will complete referral, i.e. a 50% increase in referral rate may only result in a 20 – 30% total increase in completed referrals (this will be assessed as a secondary outcome and is therefore not a component of the sample size calculation)
- ξ pre-intervention antibiotic prescription of 60% (based on informal estimates from countries, SPA data and other observational studies)
- ξ intra-cluster correlation coefficient (ICC) of 0.005 for referral and 0.05 for antimicrobial prescription

- ξ Kenya – estimated average cluster size of 230 children / month (assuming a cluster ratio of health centres : dispensaries 1:2, with 100 / month in dispensaries and 500 / month in health centres)
- ξ Senegal – estimated cluster size of 170 children per month (based on DHIS2 data on outpatient consultations in Thies in 2019)

For the referral primary outcome, we therefore initially estimated requiring the following sample size:

- ξ Kenya – 17 facilities, recruiting an average of 690 children per facility in each period, equating to 11,730 children per period
- ξ Senegal – 18 facilities, recruiting an average of 510 children per facility in each period, equating to 9,180 children per period

For the antibiotic prescription primary outcome, this would enable a minimum detectable reduction of 18% in Kenya and Senegal.

Following lower than anticipated recruitment in the pre-intervention period, sample size calculation was revised. As a result, two additional facilities were added per country and the pre-intervention period was extended from an initially anticipated 3 months to a 6 – 8 month period. A decision was also taken to target a post-intervention sample size of at least the same as the pre-intervention sample size, as well as a minimum duration of 9 months post-intervention to allow for stabilisation over time and some seasonal overlap of pre- and post-intervention periods.

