4 STATISTICAL PRINCIPLES

4.1 Confidence Intervals and p-Values

Results estimates of primary and secondary outcomes will be presented along with the associated two-sided 95% confidence intervals.

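### The cost per DALY averted has no planned uncertainty interval: only one-way percentage changes are specified, and the sampling error of the pre/post effect is not carried into the ratio

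*Protocol*

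**What the plan says.** Protocol 7.3.4 describes the calculation: "When available, effectiveness data will be combined with the cost data and cost per DALY averted will be estimated". Effectiveness is modelled from severe outcomes, including death and secondary hospitalisation, adjusted as far as possible for severity at presentation. Severity indicators and follow-up mortality are then used with published literature to predict the probability of death. Protocol 6.4.3 adds referral and secondary hospitalisation proportions, with predicted outcomes taken from literature or, where needed, expert opinion. Costs are collated in Excel.

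For uncertainty, the same section says that sensitivity analysis will "assess how the estimates would react to percentages changes in the value of the assumptions", and then: "We will undertake one-way sensitivity analysis of key parameters using the major outcome and cost parameters". It gives no percentage or range. It notes that results of this kind tend to depend most on the outcome assumptions, and leaves those to the epidemiologists' judgement. Protocol 5.8 adds a discussion of the factors that influence costs.

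Protocol 7.3, under which 7.3.4 falls, says: "We will conduct all analyses described below per country, in addition to a pooled cross-country analysis". SAP 4.1 says: "Results estimates of primary and secondary outcomes will be presented along with the associated two-sided 95% confidence intervals". The SAP mentions cost-effectiveness as a project aim but contains no analysis of it.

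**The concern.** Cost per DALY averted is a listed output, and Protocol section 4 says that the evaluation is meant to support scale-up decisions nationally and internationally. Its denominator depends on an effect estimated from a finite number of rare events. If the ratio is reported with one-way changes only, the reader learns how it responds to chosen inputs. The reader does not learn how precisely the study measured the effect, or how uncertainty in effect, cost and literature inputs combines. A country could present a favourable ratio when its own data are also compatible with no benefit or with harm, and nothing in the cost-effectiveness output would show it.

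**Working it through.** **1. What the sample size was built on.** Inputs from Protocol 6.6.1: referral 3% rising by 50% to 4.5%, alpha 0.05, power 80%, and "intra-cluster correlation coefficient (ICC) of 0.005 for referral and 0.05 for antimicrobial prescription". Two-sided testing is assumed, from SAP 4.1.

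- Children per period before clustering, pooled-variance formula with mean proportion 0.0375: n = [1.96·√(2·0.0375·0.9625) + 0.8416·√(0.03·0.97 + 0.045·0.955)]² / 0.015², which rounds up to 2,518.
- Kenya: design effect 1 + (690 − 1)·0.005 = 4.445; 2,518 × 4.445 = 11,193; 11,193 / 690 = 16.2, so 17 facilities and 17 × 690 = 11,730.
- Senegal: design effect 1 + (510 − 1)·0.005 = 3.545; 2,518 × 3.545 = 8,926; 8,926 / 510 = 17.5, so 18 facilities and 18 × 510 = 9,180.

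Both stated figures are reproduced. They rest on referral alone, with a detectable difference then quoted for antibiotics. Death and secondary hospitalisation play no part, and SAP 6.2.1 makes modelling of secondary outcomes conditional on there being enough events.

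**2. Where uncertainty is handled.**

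| Quantity | Uncertainty method stated |
|---|---|
| Primary and secondary outcomes | 95% intervals (SAP 4.1, 6.2.1) |
| Costs | Discussion of drivers (Protocol 5.8); one-way changes (7.3.4) |
| Outcome inputs to the DALY model | One-way changes, no range (7.3.4) |
| Incremental DALYs and cost per DALY averted | None beyond the one-way changes |

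The documents mention no interval, bootstrap or probabilistic analysis for the last row, and no reporting rule for an effect compatible with zero.

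**3. What a one-way change can show.** Write the ratio as ΔC/ΔD, with ΔC the incremental cost and ΔD the DALYs averted. Take ±20% as an example, since the protocol gives no figure.

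- Varying ΔD itself gives ΔC/(ΔD·(1 ± 0.2)), that is 1/1.2 = 0.83 to 1/0.8 = 1.25 times the base ratio. The sign of ΔD cannot change for any variation below 100%.
- Varying the post-period event rate instead can change the sign of the event difference, namely when RR × 1.2 exceeds 1, or RR is above 1/1.2 = 0.83.

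So what the one-way analysis reveals depends on which parameter is varied and how far. Neither is stated, and neither is tied to the study's precision.

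**4. Rough scale of sampling error in one raw input.** The documents give no rate for death or severe complication, so r is an assumption. N is the initial planned size per period, because the revised target is not given as a number. Under no effect, SE(log RR) ≈ √[2(1 − r)/(N·r)] and the 95% range is exp(±1.96·SE), ignoring clustering.

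| Assumed r | Country | Events per period (N·r) | SE | 95% range of RR |
|---|---|---|---|---|
| 0.1% | Kenya | 11.7 | 0.413 | 0.45 to 2.25 |
| 0.1% | Senegal | 9.2 | 0.467 | 0.40 to 2.50 |
| 1% | Kenya | 117.3 | 0.130 | 0.78 to 1.29 |
| 1% | Senegal | 91.8 | 0.147 | 0.75 to 1.33 |

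At 0.1% the range is far wider than ±20%; at 1% it is somewhat wider. These ranges describe raw event counts, not modelled DALYs, and serve only to show that a percentage sweep chosen without reference to the data can be narrower than the sampling error.

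**The case against.** The strongest reply is that imprecision in the clinical inputs will be visible. Severe complication is a secondary outcome. The SAP plans 95% intervals for it, reporting by country, odds ratios and risk differences where modelling is feasible (6.2.1), and counts of deaths and secondary hospitalisations (6.5). That stands: what is missing is the step from those intervals to the ratio. It also stands that no passage says in words that point estimates alone will be used, that the one-way analysis covers outcome parameters and could reach no effect if its range were wide enough, and that the work is labelled as modelled and sets no decision rule.

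A reader might go further and infer that, under this plan, an ineffective intervention would show DALYs averted in at least one country about three times in four. The documents do not support that as a finding about the plan. The figure is 1 − 0.5² = 75%, the chance that at least one of two independent, unbiased estimates falls on the favourable side when nothing is going on, reduced somewhat by ties when events are rare. A probabilistic analysis would leave it unchanged. It also requires assumed event rates, independence between countries, and no drift over time, although Protocol 6.4.1 itself warns that other events could shift mortality and morbidity. And it requires modelled DALYs to follow the sign of the raw event difference, which severity adjustment and literature-based mortality need not preserve.

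**Conclusion.** The point holds as a gap in the specified analysis. The plan propagates neither the sampling uncertainty of the pre/post effect nor the joint uncertainty in cost and literature inputs into cost per DALY averted, and its only stated method is weaker than a standard one that the collected data would support. This should be changed. It does not show that the ratio will be wrong or that favourable ratios will be claimed by chance at any particular rate. The effect on the ratio cannot be quantified from the documents, and the ranges in the working are illustrations that rest on assumed event rates, the initial sample sizes and no clustering. The conclusion rests on the absence of any uncertainty method in Protocol 5.8, 6.4.3, 7.1.4 and 7.3.4 and in the SAP; a separate health-economic analysis plan, if there is one, could already close it.

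**What to change.** In Protocol 7.3.4, or in a health-economic analysis plan to which it refers:

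- Keep the one-way analysis to identify drivers, and state which parameters are varied and over what range.
- Add a probabilistic sensitivity analysis. Either resample facilities, each with its pre and post data, or draw from the sampling distribution of the adjusted effect. Draw cost and literature inputs jointly from stated distributions.
- Report, per country and pooled, 95% uncertainty intervals for incremental cost and incremental DALYs, the cost-effectiveness plane, and net benefit or an acceptability curve.
- Where the DALY interval includes zero, present the ratio only alongside these results.
- Name the data source for each effect input. Protocol 6.4.3 and 7.3.4 refer to Day 28 hospitalisation and mortality, while the pre-post follow-up in 6.5.1 and 7.1.1 is at Day 7 with a window to Day 10. These sections need to be reconciled before a distribution can be assigned.

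The cost is some wording and programming beyond a plain Excel calculation, with no new data or participants. The result will look less certain. The change addresses sampling and input uncertainty only; it does not remove bias from changes over time between the two periods.
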